6.2.5.1 Hypomagnesemia

Hypomagnesemia is not an indication for stopping therapy. Oral or parenteral magnesium supplementation is indicated for serum magnesium levels ≤ 1.5 mEq/L (0.75 mmol/L).

6.2.5.2 Neurological Toxicity

For Grade 1 neurotoxicity, there will be no modification in the cisplatin dose. For patients with \geq Grade 2 neurotoxicity, hold the cisplatin dose

and delay for up to 2 weeks waiting for neurotoxicity to improve to < Grade 1. If neurotoxicity recovers to < Grade 1, resume therapy with a dose reduction of cisplatin by one dose level. If neurotoxicity does not improve to < Grade 1 within 2 weeks, cisplatin will be permanently discontinued. If \geq Grade 2 neurotoxicity recurs after 1 dose level reduction, cisplatin will be given at Dose Level -2 upon resolution of neurotoxicity to Grade 0-1. If \geq Grade 2 neurotoxicity recurs at Dose Level -2, or if neurotoxicity does not improve to < Grade 1 within 2 weeks, cisplatin will be permanently discontinued.

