11.2 Sample Size Considerations

The primary outcome measure for this trial is treatment completion rate. A treatment completion rate of 70% or above would be sufficient to consider this regimen for further study. To test the null hypothesis that the treatment completion rate is 0.50 against the alternative that it is 0.70 at the one-sided 0.0510 level with 0.90 power will require 38 evaluable patients. To allow for potential 15% dropout, 45 patients will be enrolled in the study.

We will recruit 45 participants from the AMC core sites in Africa over an estimated 2 year period of time and have a minimum of 1 year of follow-up. We anticipate that at least 50% of recruited participants will be Stage 3 and 4. This will be helpful in stratified analyses by stage and node positivity.

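### The rule for neurotoxicity recurring after one cisplatin dose reduction both resumes and permanently stops cisplatin for a woman at Grade 1 two weeks into the recurrence

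*Combined protocol and SAP*

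**What the plan says.** Section 6.2.5.2 has six sentences.

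1. Grade 1: "For Grade 1 neurotoxicity, there will be no modification in the cisplatin dose".
2. Grade 2 or worse: hold cisplatin and "delay for up to 2 weeks waiting for neurotoxicity to improve to < Grade 1".
3. Resuming: "If neurotoxicity recovers to < Grade 1, resume therapy with a dose reduction of cisplatin by one dose level".
4. Stopping: "If neurotoxicity does not improve to < Grade 1 within 2 weeks, cisplatin will be permanently discontinued".
5. Grade 2 or worse again after one dose-level reduction: "cisplatin will be given at Dose Level -2 upon resolution of neurotoxicity to Grade 0-1". This sentence gives no time limit.
6. Two triggers for a permanent stop. One is recurrence of Grade 2 or worse at Dose Level -2. The other is "or if neurotoxicity does not improve to < Grade 1 within 2 weeks, cisplatin will be permanently discontinued".

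Section 11.2 states: "The primary outcome measure for this trial is treatment completion rate". Section 11.1 estimates it as the women who complete cisplatin divided by the women who start it. Section 9.1.1 defines it as completing the cisplatin/RT regimen among those enrolled. Neither section says how many cycles count as completion. Section 4.2.2 plans six weekly cycles, on days 1 to 36.

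**The concern.** Sentences 5 and 6 use different recovery grades for what appears to be the same episode. Sentence 5 accepts Grade 1 as recovered. Sentence 6 does not, and its consequence is permanent withdrawal of the study drug. The trial runs at several African sites, and two sites could treat identical findings in opposite ways while each followed the protocol.

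Two things are at stake. The first is a safety rule that cannot be applied as stated. The second is the analysis. A permanent stop bears on the numerator of the primary outcome. It also bears on the dose delays, reductions and missed doses that section 9.1.4 uses to judge safety and tolerability.

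**Working it through.** The plan gives no figure on this point to reproduce. The check is a reading of section 6.2.5.2 sentence by sentence, followed by the timing.

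**Step 1: recovery grades.** Below Grade 1, meaning Grade 0, is required in four sentences (2, 3, 4 and 6). Grade 0-1 is accepted in one (5).

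**Step 2: what happens at two weeks after a hold.**

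| Grade at two weeks | First episode | Recurrence after one reduction |
|---|---|---|
| 0 | Resume one level lower (sentence 3) | Resume at Dose Level -2 (sentence 5) |
| 1 | Stop (sentence 4) | Resume (sentence 5) **and** stop (sentence 6) |
| 2 or worse | Stop (sentence 4) | Stop (sentence 6) |

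The first-episode column is consistent. The clash is in one cell only.

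**Step 3: can sentence 6 be read so that it does not apply?** Its two-week clause needs an episode to act on. Sentence 4 already covers the first episode. Recurrence at Dose Level -2 is already a stop trigger in sentence 6 itself. The clause adds something only for the recurrence in sentence 5, so that is its natural target.

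**Step 4: link to the primary outcome.** A permanent stop can make a woman a non-completer under section 11.1. One woman classified differently moves the rate by 1/38 = 2.6 percentage points if the denominator is the 38 evaluable women of section 11.2, or 1/45 = 2.2 points if it is all 45 enrolled. This is the step per woman, not an expected effect.

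**Step 5: how often the clash could change her status.** She must reach Grade 2 or worse, recover to Grade 0 within two weeks, resume at a lower dose, reach Grade 2 or worse again, and then be at Grade 1. Without delay, dose six falls on day 36. Section 6.2.6 bars chemotherapy after radiotherapy ends, and section 4.6.1.3 limits radiotherapy to 56 days. I assume that held doses are moved later rather than omitted, and that radiotherapy continues during the hold, as section 6.2.3 generally provides.

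- First hold 7 days, second hold the full 14: 36 + 7 + 14 = day 57, after day 56. If completion means six doses, she is a non-completer under either sentence.
- First hold 7 days, Grade 1 reached and drug resumed 7 days into the second hold: 36 + 7 + 7 = day 50. She could complete under sentence 5. If still at Grade 1 at two weeks, she would be stopped under sentence 6.
- In general the choice of sentence can matter when total delay is at most 56 − 36 = 20 days. It can also matter if radiotherapy overruns (section 6.1 calls 56 days a goal) or if fewer than six cycles count as completion.

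**The case against.** Three arguments have weight.

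**The symbol may be misread.** If each less-than sign were really less-than-or-equal, every sentence would agree with Grade 0-1 and the point would disappear. The two symbols do vary in this file: the summary of changes prints a CD4 count below 200 where the current synopsis prints 200 or below. That difference is not itself an error. It shows only that the symbols deserve a check. Against the misreading, the sign is the same in all four places, the greater-than-or-equal signs survive in the same paragraph, and a less-than-or-equal sign before Grade 1 survives in section 6.2.5.4.1. A misreading is possible but unlikely.

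**Sentence 6 may be read narrowly.** Someone could treat its two-week clause as a repeat of sentence 4. The direct clash then goes, but Grade 1 at two weeks would end cisplatin after a first episode and permit it after a second, with no reason given and no time limit for the second.

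**Few women could be affected.** This stands, as the timing above shows.

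A reader might also infer that Grade 1 is contradictory throughout the section, including at onset. The documents do not support that. Sentence 1 concerns toxicity that has not reached Grade 2, and the others concern recovery after it has. A rule may set different grades for holding and for resuming, and both can be followed.

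**Conclusion.** Wrong as written, within a narrow scope. For Grade 2 or worse neurotoxicity recurring after one dose-level reduction, section 6.2.5.2 contradicts itself for a woman at Grade 1 at two weeks. The first-episode sentences are consistent with each other but set a different recovery grade from the recurrence sentence. The conclusion assumes that the symbols are printed correctly and that the final clause applies to the recurrence.

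The effect on the primary outcome is possible, unquantified and probably small. It follows from section 11.1 and is not stated in section 6.2.5.2.

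A reader might infer that this wording could decide the trial's result. With n = 38 and a null rate of 0.50, the exact one-sided tails are P(X ≥ 24) = 0.0717 and P(X ≥ 25) = 0.0365, on either side of the stated 0.0510 level. Those figures are correct, but they hold for any woman reclassified for any reason. They do not show that this rule would reclassify anyone. Nor do the documents show that sites would in fact act differently, only that the text allows it. The case for correction rests on a permanent-stop rule that cannot be followed as stated.

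**What to change.** First, check the comparison symbols in section 6.2.5.2 against the sponsor's master file. If the clash remains, reconcile the recurrence sentence with the final sentence and check both against the first-episode sentences. Each episode should then have one unambiguous recovery grade and one time limit for resuming or stopping. If the episodes are meant to differ, say so. The choice of grade and time limit is for the clinical team, and none is proposed here.

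The cost is a one-paragraph clarification, approved as section 12.2 requires for any protocol change. It needs no change to the design, sample size or analysis method.

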6.2.5.3 Ototoxicity

Discontinue cisplatin for \geq grade 3 ototoxicity.

6.2.5.4 Allergic Reactions

Discontinue cisplatin if \geq grade 3 anaphylaxis occurs.

6.2.5.4.1 Other Grade 3/4 Non-Hematologic Toxicity

If a patient develops Grade 3 or 4 non-hematologic toxicity not detailed above (excluding nausea, vomiting, anorexia, fatigue, fever without Grade 3/4 neutropenia or alopecia), hold cisplatin therapy. Treatment can be restarted if the toxicity has resolved to \leq Grade 1 by the time of the next treatment. Subsequent doses of cisplatin should then be reduced by 1 dose level.

6.2.6 Completion of Chemotherapy

If all 6 cycles of chemotherapy cannot be administered during external radiotherapy (whole pelvis and parametrial boost), the 6th cycle should be given during brachytherapy but not on the same day as brachytherapy.

Chemotherapy may not be given after completion of radiotherapy.

7.0 ADVERSE EVENTS MONITORING AND REPORTING

This study will utilize the Common Terminology Criteria for Adverse Event (CTCAE) version 4.0 for adverse event reporting. A copy of the CTCAE version 4.0 can be downloaded from the CTEP home page (<http://ctep.cancer.gov>). All appropriate treatment areas should have access to a copy of the CTCAE version 4.0. The document “NCI Guidelines: Adverse Event Reporting Requirements for NCI Investigational Agents” clearly outlines reporting criteria.

This study will be monitored by the Clinical Data Update System (CDUS). Cumulative CDUS data will be submitted quarterly to CTEP by electronic means. Reports are due January 31, April 30, July 31, and October 31.

7.1 Classification of AEs by Severity and Relationship to Study Drug Administration

The Common Terminology Criteria for Adverse Events (CTCAE) is designed as an instrument to be used to document AEs identified through a combination of clinical and laboratory evaluation. CTCAE is NOT a tool to assist with data extraction from source documents without the direct participation and supervision of clinical investigators. AE grading and assignment of attribution require documentation by medical personnel who are directly involved in the clinical care of protocol subjects.

Each CTCAE term in the current version is a unique representation of a specific event used for medical documentation and scientific analysis and is a single MedDRA Lowest Level Term (LLT). Grade is an essential element of the Guidelines and, in general, relates to severity for the purposes of regulatory reporting to NCI as follows:

Grade	Description
0	No AE (or within normal limits)
1	Mild; asymptomatic or mild symptoms; clinical or diagnostic observations only; intervention not indicated
2	Moderate; minimal, local, or noninvasive intervention (e.g., packing, cauter) indicated; limiting age-appropriate instrumental activities of daily living (ADL)
3	Severe or medically significant but not immediately life-threatening; hospitalization or prolongation of hospitalization indicated; disabling; limiting self-care ADL
4	Life-threatening consequences; urgent intervention indicated
5	Death related to AE

NOTE: A severe AE, as defined by the above grading scale, is NOT the same as serious AE which is defined below (FDA, 21 CFR 312.32; ICH E2A and ICH E6).

Adverse Event

Any untoward medical occurrence associated with the use of a drug in humans, whether or not considered drug related. Therefore, an AE can be ANY unfavorable and unintended sign (including an abnormal laboratory finding), symptom, or disease temporally associated with the use of a medicinal (investigational) product, whether or not considered related to the medicinal (investigational) product (attribution of unrelated,

unlikely, possible, probable, or definite). (International Conference of Harmonization [ICH] E2A, E6).

Life-Threatening Adverse Event

Any AE that places the patient or subject, in view of the Investigator, at immediate risk of death from the reaction. It does NOT include an AE that, had it occurred in a more severe form, might have caused death (FDA 21 CFR 312.32, ICH E2A).

Serious Adverse Event (SAE)

Any adverse drug event (experience) occurring at any dose that results in ANY of the following outcomes:

- 1) Death.
- 2) A life-threatening adverse drug experience.
- 3) Inpatient hospitalization or prolongation of existing hospitalization (for >24 hours).
- 4) A persistent or significant incapacity or substantial disruption of the ability to conduct normal life functions
- 5) A congenital anomaly/birth defect.
- 6) Important Medical Events (IME) that may not result in death, be life-threatening, or require hospitalization may be considered a serious adverse drug experience when, based upon medical judgment, they may jeopardize the patient or subject and may require medical or surgical intervention to prevent one of the outcomes listed in this definition (FDA, 21 CFR 312.32; ICH E2A and ICH E6).

Please note for hospitalization – All hospitalizations (or prolongation of existing hospitalization) for medical events that result in an inpatient hospital stay equal to or greater than 24 hours must be reported regardless of the requirements for Phase of study, expected or unexpected, and attribution. Hospitalization is used as an indicator of the seriousness of the AE and should ONLY be used for situations where the AE truly fits this definition and NOT for hospitalizations associated with less serious events. For example, a hospital visit where a patient is admitted for observation or minor treatment such as hydration and released in less than 24 hours should not be reported, but do report an admission for a myocardial infarction.

Toxicity

Toxicity is a term NOT clearly defined by regulatory organizations. Toxicity has been described as an AE that has an attribution of possibly, probably or definitely related to investigational treatment. To minimize confusion the NCI would recommend that the term toxicity NOT be utilized for AE reporting purposes. The CTCAE continues to use the term ‘toxicity’ because of familiarity.

Expectedness (Unexpected Adverse Event)

An unexpected AE is any AE, the specificity or severity of which is not consistent with the Instructions for Use or other documentation; or, if an IB or equivalent is not required or available, the specificity or severity of which is not consistent with the risk

information described in the general investigational plan. Additionally the ICH E2A defines an unexpected adverse drug reaction as an AE, the nature and severity of which is not consistent with the applicable product information (for example, Investigator's Brochure for investigational agent). The investigator shall report all SAEs immediately to the sponsor except for those that the protocol identifies as not requiring immediate reporting (EC Directive of 2001; Article 16, #1).

CTEP Adverse Event Reporting System (CTEP-AERS)

An electronic system for expedited submission of AE reports is available at <https://eapps-ctep.nci.nih.gov/ctepaers/>. A username and password are not required for this system.

Attribution

An assessment of the relationship between the AE and the medical intervention. CTCAE does not define an AE as necessarily "caused by a therapeutic intervention." After naming and grading the event, the clinical investigator must assign an attribution to the AE using the following attribution categories:

Relationship	Attribution	Description
Unrelated to investigational agent/intervention ¹	Unrelated	The AE is clearly NOT related to the intervention
	Unlikely	The AE is doubtfully related to the intervention
Related to investigational agent/intervention ¹	Possible	The AE may be related to the intervention
	Probable	The AE is likely related to the intervention
	Definite	The AE is clearly related to the intervention

¹NOTE: AEs listed as "possibly, probably, or definitely" related to the investigational agent/intervention in CTEP-AERS are considered to have a suspected "reasonable causal relationship" to the investigational agent/intervention (ICH E2A). For routine, CDUS adverse event reporting purposes, "Attribution" defines the relationship between the adverse event and the investigational agent(s)/intervention as defined in Clinical Data Update System (CDUS) Instructions and Guidelines that can be found at: http://ctep.cancer.gov/protocolDevelopment/electronic_applications/docs/cdus_ig_3r4.pdf.

7.2 Expedited AE Reporting Procedures

Expedited AE reporting for this study must use CTEP-AERS, accessed via the CTEP home page (<http://ctep.cancer.gov>). The reporting procedures to be followed are presented in the CTEP, NCI Guidelines: Adverse Event Reporting Requirements which can be downloaded from the CTEP home page (<http://ctep.cancer.gov>). These requirements are briefly outlined in the table below.

CTEP-AERS is programmed for automatic electronic distribution of reports to the following individuals: Study Coordinator of the Lead Organization, Principal Investigator, and the local treating physician. CTEP-AERS provides a copy feature for other e-mail recipients.

Expedited Reporting Requirements for AEs that occur within 30 Days of Last Protocol Treatment

Commercial Agent Studies: Expedited Reporting Requirements for Adverse Events that Occur in a Non-IND/IDE trial within 30 Days of the Last Administration of a Commercial Agent 1, 2

FDA REPORTING REQUIREMENTS FOR SERIOUS ADVERSE EVENTS (21 CFR Part 312)

NOTE: Investigators **MUST** immediately report to the sponsor (NCI) **ANY** Serious Adverse Events, whether or not they are considered related to the investigational agent(s)/intervention (21 CFR 312.64)

An adverse event is considered serious if it results in **ANY** of the following outcomes:

- 1) Death
- 2) A life-threatening adverse event
- 3) An adverse event that results in inpatient hospitalization or prolongation of existing hospitalization for \geq 24 hours
- 4) A persistent or significant incapacity or substantial disruption of the ability to conduct normal life functions
- 5) A congenital anomaly/birth defect.
- 6) Important Medical Events (IME) that may not result in death, be life threatening, or require hospitalization may be considered serious when, based upon medical judgment, they may jeopardize the patient or subject and may require medical or surgical intervention to prevent one of the outcomes listed in this definition. (FDA, 21 CFR 312.32; ICH E2A and ICH E6).

ALL SERIOUS adverse events that meet the above criteria **MUST** be immediately reported to the NCI via CTEP-AERS within the timeframes detailed in the table below.

Hospitalization	Grade 1 Timeframes	Grade 2 Timeframes	Grade 3 Timeframes	Grade 4 & 5 Timeframes
Resulting in Hospitalization \geq 24 hrs	10 Calendar Days			24-Hour 5 Calendar Days
Not resulting in Hospitalization \geq 24 hrs	Not required		10 Calendar Days	

Expedited AE reporting timelines are defined as:

- “24-Hour; 5 Calendar Days” - The AE must initially be reported via CTEP-AERS within 24 hours of learning of the AE, followed by a complete expedited report within 5 calendar days of the initial 24-hour report.
- “10 Calendar Days” - A complete expedited report on the AE must be submitted within 10 calendar days of learning of the AE.

Serious adverse events that occur more than 30 days after the last administration of investigational agent/intervention and have an attribution of possible, probable, or definite require reporting as follows:

Expedited 24-hour notification followed by complete report within 5 calendar days for:

All Grade 4 and Grade 5 AEs

Expedited 10 calendar day reports for:

Grade 2 adverse events resulting in hospitalization or prolongation of hospitalization

Grade 3 adverse events

NOTE: Deaths clearly due to progressive disease should **NOT** be reported via CTEP-AERS but rather should be reported via routine reporting methods (e.g., CDUS and/or CTMS).

Note: A death on study requires both routine and expedited reporting regardless of causality, unless as noted in the above table. Attribution to treatment or other cause must be provided.

Expedited AE reporting timelines defined:

“24 hours; 5 calendar days” - The Investigator must initially report the AE via CTEP-AERS, according to the procedures outlined in section 6.2, within 24 hours of learning of the event, and followed by a complete AE report submitted via CTEP-AERS within 5 calendar days of the initial 24-hour report. Use the NCI protocol number and

protocol-specific subject ID assigned during trial registration on all reports. In the rare event when Internet connectivity is disrupted, a 24-hour notification is to be made to NCI by telephone at: [contact], or [contact] for CIP studies. An electronic CTEP-AERS report MUST be submitted immediately upon re-establishment of internet connection.

“10 calendar days”— A complete CTEP-AERS report on the AE must be submitted within 10 calendar days of the Investigator learning of the event. Use the NCI protocol number and protocol-specific subject ID assigned during trial registration on all reports.

Any medical event equivalent to CTCAE Grade 3, 4, or 5 that precipitates hospitalization (or prolongation of existing hospitalization) must be reported regardless of attribution and designation as expected or unexpected with the exception of any events identified as protocol-specific expedited AE reporting exclusions.

Any event that results in persistent or significant disabilities/incapacities, congenital anomalies, or birth defects must be reported via CTEP-AERS according to the guidelines as described above.

7.2.1 National and Local Adverse Event Reporting

All Grade 4 related and unexpected events and all Grade 5 events are communicated to the study chair and regulatory agencies as mandated in this protocol. These reports are reviewed by the study chair (or designated co-chair) within two working days for considerations of amendments.

7.3 Routine AE Reporting

All AEs reported through CTEP-AERS must also be reported in routine study data submissions using the Adverse Event electronic case report form (eCRF). All AEs, except for expected Grade 1 events listed below, should be reported. All deaths that occur on study should be reported in the Adverse Event form and the Death Form, regardless of attribution to the protocol agents.

The following grade 1 AEs will not require reporting in the Adverse Event eCRF.

Grade 1 Expected Adverse Events for Radiation Therapy (listed by CTCAE Category and term):

GASTROINTESTINAL DISORDERS: diarrhea, proctitis, rectal pain

INJURY, POISONING AND PROCEDURAL COMPLICATIONS: dermatitis radiation

RENAL AND URINARY DISORDERS: urinary tract pain, cystitis noninfectious

REPRODUCTIVE SYSTEM AND BREAST DISORDERS: dyspareunia, pelvic pain, vaginal pain

SKIN AND SUBCUTANEOUS TISSUE DISORDERS: skin hyperpigmentation, skin hypopigmentation, alopecia

Grade 1 Expected Adverse Events for Cisplatin:

BLOOD AND LYMPHATIC SYSTEM DISORDERS: anemia

EAR AND LABYRINTH DISORDERS: tinnitus

GASTROINTESTINAL DISORDERS: nausea, constipation, diarrhea, abdominal pain

GENERAL DISORDERS AND ADMINISTRATION SITE CONDITIONS: fatigue

INVESTIGATIONS: creatinine increased, weight loss

METABOLISM AND NUTRITION DISORDERS: anorexia

NERVOUS SYSTEM DISORDERS: dysgeusia, paresthesia

SKIN AND SUBCUTANEOUS TISSUE DISORDERS: alopecia

